##### 3.2.2 Ixabepilone administration and dosage

Ixabepilone will be given on days 1, 2, 3, 4, and 5 of each three week cycle as a one hour intravenous infusion. The dose will be 6 mg/m^2/day on five successive days. For ixabepilone preparation instructions, see Section 8, Pharmaceutical Information.

##### 3.2.3 Potential for hypersensitivity reactions related to Cremophor®EL

**Premedication:** All patients must be pre-medicated before each administration of ixabepilone to prevent a hypersensitivity reaction.

- **Regimen 1** described below is the pre-medication regimen recommended for routine use.

- If a patient experiences a hypersensitivity reaction with oral H1 and H2 blockers (Regimen 1) then the patient, if re-treated, should be pre-medicated according to **Regimen 2** below. See the section **3.2.4** below for immediate management of reactions.
- If a subject continues to experience a HSR with Regimen 2 then the subject, if retreated, the patient should be pre-medicated according to the recommended **Regimen 3**.
- **Regimen 4** is suggested as the approach for re-treatment with ixabepilone after a Grade 2 or greater HSR despite premedication with Regimen 1, 2 or 3.

**Regimen 1:** Premedicate approximately one hour prior to the infusion of ixabepilone with:

- a) Oral H1 antagonist (may consist of diphenhydramine 50 mg or equivalent H1 antagonist) and
- b) Oral H2 antagonist (may consist of ranitidine 150 - 300 mg or cimetidine 300 - 800 mg or nizatidine 150 - 300 mg or famotidine 20 - 40 mg or another H2 antagonist)

Note: In the event a given patient does not tolerate the specified antihistamines, alternatives may be substituted at the Investigator's discretion. In addition, if the specified antihistamine is not available, alternatives may be substituted including IV formulations

**Regimen 2:** Premedicate approximately 30 - 45 minutes prior to each infusion of ixabepilone with:

- a) Dexamethasone 20 mg IV (or equivalent)
- b) Diphenhydramine 50 mg IV (or equivalent), and
- c) Ranitidine 50 mg IV (or equivalent).

**Regimen 3:** Premedicate with:

- a) Dexamethasone 20 mg po administered, approximately 12 and 6 hours prior to the infusion of ixabepilone,
- b) Diphenhydramine 50 mg IV, approximately 30 - 45 minutes prior to each infusion of ixabepilone,
- c) Cimetidine 300 mg IV or ranitidine 50 mg IV (or equivalent), approximately 30 - 45 minutes prior to each infusion of ixabepilone.

**Regimen 4:** A suggested approach for re-treatment with ixabepilone after a Grade 2 or greater HSR despite premedication with Regimen 1, 2 or 3 is as follows:

- a) Dexamethasone 20 mg IV or p.o. (or equivalent) every 6 hours for 4 doses with the last dose administered 30 minutes before rechallenge with ixabepilone; With the last dexamethasone dose begin:
  - Diphenhydramine 50 mg IV (or equivalent) 30 minutes before ixabepilone,
  - Cimetidine 300 mg or ranitidine 50 mg IV (or equivalent) 30 minutes before ixabepilone.
- b) Begin ixabepilone at 25% of the previous rate for 1 hour;
- c) Increase rate gradually to complete the total infusion within 6 hours from the time the drug was initially diluted.

### 3.2.4 Immediate management of Allergic/Hypersensitivity Reaction

Allergic/Hypersensitivity Reaction (transient rash, drug fever < 38°C): Supervise without further treatment. If progression of symptom(s) is(are) noted, follow the guidelines described below.

Allergic/Hypersensitivity Reaction (urticaria, drug fever greater than or equal to 38°C and/or asymptomatic bronchospasm): Interrupt the infusion. Administer additional doses of H1 and/or H2 blockers intravenously as needed. Typically 25 mg diphenhydramine IV is sufficient to relieve symptoms. If symptoms abate, attempt re-infusion at a slower rate, as detailed. Restart the remaining infusion at one quarter the hourly rate x 15 minute, then increase the rate to one half the hourly rate x 15 minutes, then increase the rate to complete the remaining infusion within one hour of the restart time. If the symptoms recur, discontinue infusion and follow guidelines below.

Subsequent Infusions following Allergic/Hypersensitivity Reactions:

When a patient experiences an allergic/hypersensitivity reaction and is able to resume the infusion without recurrence of the reaction, the following day's infusion will be given according to the following rate schedule: First start the infusion at one quarter the hourly rate x 15 minutes, then increase the rate to one half the hourly rate x 15 minutes, then increase the rate to complete the remaining infusion within one hour of the start time. If the patient does not have another reaction, the subsequent infusions may be given at the full hourly rate from the start of the infusion. No additional H1 or H2 blockers are indicated for these doses, beyond the standard premedications administered 30 to 60 minutes before the administration of ixabepilone. Consultation with study team is indicated to determine if steroids are indicated per Regimen 2.

Recurrent CTCAE Grade 2 or CTCAE Grade 3 or 4 Allergic/Hypersensitivity Reactions: Stop the infusion. Administer additional doses of H1 and H2 blockers intravenously. Administer IV steroids (see discussion below) and consider epinephrine and bronchodilators as clinically indicated. Further treatment should be delayed 24 hours. Prior to re-challenge and with all subsequent cycles, give both an H1 and H2 blocker intravenously plus dexamethasone 20 mg x 2 doses (orally or intravenously) 12 and 6 hours pre ixabepilone. Dexamethasone could be used at the investigator's discretion in subsequent cycles for recurrent (i.e. occurring despite slowing infusion as discussed above) grade 2 reactions but is not mandated.

Grade 4 (anaphylaxis): Discontinue therapy. Do not attempt re-challenge.

Note: The administration of dexamethasone immediately prior to ixabepilone is unlikely to be effective.

Note: If dexamethasone is administered, it will initially be administered prior to all doses. However, since dexamethasone has a long half-life, and since daily administration would mean patients would receive 100 mg or more of dexamethasone every three weeks, a dose reduction to 5 mg dexamethasone administered intravenously prior to each dose of ixabepilone may be attempted at the discretion of the Principal Investigator. Please note that the above regimens 1 – 4 are standard for ixabepilone that is given as a one day infusion every 3 weeks, not a daily x 5 schedule. The decision to administer this regimen will be guided by: (1) the severity of the initial reaction that prompted the use of dexamethasone; (2) the patient's reaction to

ixabepilone after the institution of dexamethasone premedication; and (3) the number of additional cycles the patient is anticipated to receive. Regarding the latter, if a patient appears to be responding to the treatment and it is anticipated that he/she will receive several more cycles, then in such a patient attempts to reduce the steroid dose would be beneficial.

Note: Dexamethasone premedication may be used, if in the opinion of the Principal Investigator such precaution should be taken. For example, in a patient with a prior history of sensitivity to paclitaxel or cyclosporin.

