Finally, based on the presence of Cremophor® EL in the formulation of ixabepilone, the potential for hypersensitivity reactions exists with intravenous administration of this compound. Although the quantity of Cremophor® EL in ixabepilone is equivalent to three times that in the same dose of Taxol®, its greater potency has resulted in a Cremophor® EL to total volume that is less than that achieved when Taxol®, which includes Cremophor® EL in its formulation, has been administered (15). In clinical trials, anaphylaxis and severe hypersensitivity reactions (dyspnea, hypotension requiring treatment, angioedema, and generalized urticaria) have occurred in 2% of patients receiving Taxol®. It is not known whether the hypersensitivity reaction is due to paclitaxel, Cremophor® EL, or both. The reported incidence of anaphylaxis with other Cremophor® EL-containing compounds is much lower than with Taxol® (16). For example, cyclosporine for injection has rarely been associated with anaphylactic reactions (approximately 1 in 1,000). Although the low incidence of anaphylactic reactions with Cremophor® EL containing compounds other than Taxol®, suggest this may not be a significant problem, some cases of hypersensitivity have been reported with ixabepilone but the incidence of this has been very low and very rare in the NCI experience with a daily administration on 5 consecutive days. Prophylaxis for hypersensitivity reactions has been similar to the “standard” Taxol® pre-medication regimen but has not included steroids; instead consisting of the following: (1) diphenhydramine 50 mg IV, 30 to 60 minutes before the administration of ixabepilone; and (2) cimetidine 300 mg or ranitidine 50 mg IV, 30 to 60 minutes before the administration of ixabepilone.

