**Store the Vehicle for Constitution in the refrigerator or at room temperature (2°C to 25°C).**

#### 8.1.9 Stability

Shelf life surveillance is ongoing. After initial constitution with the accompanying diluent, the product may be stored for a maximum of one (1) hour at room temperature and room light. **After final dilution in Lactated Ringers for Injection (LRI) to concentrations between 0.2 and 0.6 mg/mL, the drug product is stable at room temperature and light for a maximum of 6 hours.**

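### After a hypersensitivity reaction, the next day's stepped infusion must still finish within one hour, so its last step averages at least 162.5% of the standard rate

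*Combined protocol and SAP*

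**What the plan says.** Section 3.2.2 sets the standard infusion: "Ixabepilone will be given on days 1, 2, 3, 4, and 5 of each three week cycle as a one hour intravenous infusion", at 6 mg/m² per day. Section 3.3.1 allows one reduction, to 4.5 mg/m² per day.

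Section 3.2.4 has two stepped schedules for patients whose infusion was interrupted for a reaction (urticaria, drug fever of at least 38°C or asymptomatic bronchospasm):

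- **Same-day restart.** One quarter of the hourly rate for 15 minutes, one half for 15 minutes, "then increase the rate to complete the remaining infusion within one hour of the restart time".
- **Following day**, for a patient who "is able to resume the infusion without recurrence of the reaction". The same two slow steps, "then increase the rate to complete the remaining infusion within one hour of the start time".

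If the following-day infusion passes without a reaction, later infusions return to the full hourly rate from the outset. The section adds no H1 or H2 blockers for these doses beyond standard premedication and leaves steroids to consultation with the study team. It states no maximum rate for the last step and does not define *hourly rate*. A later paragraph of the section, on recurrent reactions, describes the preceding approach as a slowing of the infusion.

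**The concern.** A full dose that normally takes one hour cannot be started slowly and still finish in one hour unless the last part runs faster than usual. The following-day schedule has exactly that structure. Over the whole hour the mean rate is unchanged, so the first half is slowed and the second half is accelerated.

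At stake is the safety of the few patients who reacted the day before. They would receive drug and Cremophor EL at a higher peak rate than patients who never reacted. The section also treats 100% of the hourly rate as what a patient returns to after tolerating the stepped infusion, yet by then the patient has already been run well above it.

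**Working it through.** The protocol states no rate for the last step, so there is no figure of its own to reproduce. The check is a mass balance.

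**Inputs**

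- Dose 6 mg/m² over 1 h (3.2.2), so the standard rate R = 6 mg/m²/h. At the reduced dose (3.3.1), R = 4.5 mg/m²/h.
- Step 1: 0.25 R for 15 min. Step 2: 0.50 R for 15 min. Step 3: the remainder, finished no later than 60 min after the start (3.2.4).

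**Following-day infusion**

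- Fraction given in the first 30 min: 0.25 × 15/60 + 0.50 × 15/60 = 0.0625 + 0.125 = 0.1875, which is 1.125 mg/m² of 6.
- Fraction left: 1 − 0.1875 = 0.8125, which is 4.875 mg/m².
- Time left: at most 30 min.
- Minimum mean rate of step 3: 0.8125 / 0.5 h = 1.625 R. This is 1.625 × 6 = 9.75 mg/m²/h, or 1.625 × 4.5 = 7.31 mg/m²/h at the reduced dose.

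Finishing before the hour is up only raises this rate, so 162.5% is a minimum.

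**Same-day restart**

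Suppose the reaction occurs t minutes into a standard infusion. The fraction still to be given is f = 1 − t/60. The minimum mean rate of step 3 depends on what *hourly rate* means:

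- Standard rate (full dose per hour): (f − 0.1875)/0.5. This exceeds 100% only if f > 0.6875, that is t < 18.75 min.
- Remaining dose per hour: 1.625 f. This exceeds 100% only if f > 0.615, that is t < 23.1 min.

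| Reaction at (min) | f | Step 3, *hourly rate* = standard | Step 3, *hourly rate* = remaining dose per hour |
|---|---|---|---|
| 5 | 0.917 | 146% | 149% |
| 10 | 0.833 | 129% | 135% |
| 15 | 0.750 | 113% | 122% |
| 18.75 | 0.6875 | 100% | 112% |
| 30 | 0.500 | 63% | 81% |

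If the full hour is used, the average rate over a restart is f, always below 1. The protocol is therefore right to call the restart slower on average. Only an early reaction forces its last step above the original rate.

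**With the last step capped at 100%**

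- Following day: 30 + 0.8125 × 60 = 78.75 min, or 18.75 min more than now.
- Same-day restart (*hourly rate* = standard): 30 + (f − 0.1875) × 60 = 78.75 − t min. For reactions at 5, 10 and 15 min this is 73.75, 68.75 and 63.75 min.

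**The case against.** The best case against concedes the arithmetic and disputes its consequence.

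- **Faster rates have been given.** Section 1.2.4 reports 40 mg/m² over 3 hours (40/3 = 13.3 mg/m²/h) and, in one breast cancer study, 50 mg/m² over 3 hours (16.7 mg/m²/h) or 1 hour (50 mg/m²/h). So 9.75 mg/m²/h is not unusual for this drug. That stands, but those patients were not selected for a reaction the day before.
- **Few patients are affected.** The rule needs a reaction, a successful restart and a dose due the next day. Section 1.2.4 says of hypersensitivity that "the incidence of this has been very low and very rare in the NCI experience with a daily administration on 5 consecutive days". This stands and limits the urgency.
- **Harm is inferred.** The protocol does not say that a high rate late in an infusion provokes reactions, and the patient reaches the fast step only after 30 minutes at reduced rates. This also stands; no harm is demonstrated.
- **Other safeguards exist.** Section 3.2.3 moves a re-treated patient who reacted on Regimen 1 to Regimen 2, which includes dexamethasone, and Regimen 4 offers a slower re-treatment. This stands in part. Section 3.2.4 says that Regimens 1 to 4 were standard for one-day dosing every three weeks, and it doubts the value of dexamethasone given just before the infusion. None of these safeguards caps the rate in the following-day schedule.
- **The fix reaches too far.** A restart after a reaction at 30 minutes could run its last step at 63% today, whereas a 100% ceiling would let it finish in 48.75 minutes. This does not stand. One hour is a maximum time in the current text, so any faster last step is already allowed, and a ceiling can only tighten that.

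If the hour were counted from the beginning of the third step, the last step would need only 81.25% of the standard rate. The wording does not support this. The schedule opens with the start of that day's infusion, and the same-day paragraph counts from the restart in the same way.

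**Conclusion.** The concern holds. Followed as written, the following-day schedule requires a last step averaging at least 162.5% of the standard rate at either dose level, with no ceiling. This rests on *start time* meaning the start of that day's infusion and on *hourly rate* meaning the full dose per 60 minutes; for a full dose, both definitions of *hourly rate* coincide. The same-day restart has the same uncapped step, but exceeds the original rate of necessity only after a reaction in roughly the first 19 to 23 minutes.

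This is a safety wording error that will rarely come into play. It should be fixed because the rule defeats its own purpose in the patients it is meant to protect. It has no bearing on the sample size or error rates, and no effect on response counts is shown.

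**What to change.** In both paragraphs of section 3.2.4:

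1. Define *hourly rate* as the standard rate, the full daily dose per 60 minutes.
2. Replace the third step with: then no faster than the standard hourly rate until the dose is complete, within 6 hours of final dilution.
3. State the resulting time at that ceiling: about 80 minutes from the start for a full next-day dose, and no more than that from the restart for a same-day restart.

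Drug handling permits this. Section 8.1.9 says that after final dilution "the drug product is stable at room temperature and light for a maximum of 6 hours". Regimen 4 in section 3.2.3 already works to the same limit: "Increase rate gradually to complete the total infusion within 6 hours from the time the drug was initially diluted".

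The cost is one sentence in each of two paragraphs, and about 19 extra minutes of chair time for a next-day dose (up to about 19 for an early same-day restart), only in the few patients who react.

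### The stepped infusion given the day after a hypersensitivity reaction must still finish within one hour, which forces its last 30 minutes to at least 162.5% of the standard rate

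*Combined protocol and SAP*

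**What the plan says.** Section 3.2.2 gives the drug on Days 1 to 5 "of each three week cycle as a one hour intravenous infusion". The standard hourly rate is therefore one full daily dose per hour: 6 mg/m²/h at the starting dose and 4.5 mg/m²/h at the single reduced level in section 3.3.1.

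Section 3.2.4 has two stepped schedules.

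- **Same-day restart.** After an interruption for urticaria, fever or asymptomatic bronchospasm, the instruction is "If symptoms abate, attempt re-infusion at a slower rate, as detailed". The steps are 25% of the hourly rate for 15 minutes and 50% for 15 minutes, and "then increase the rate to complete the remaining infusion within one hour of the restart time".
- **Next-day infusion.** This applies when the patient "is able to resume the infusion without recurrence of the reaction". It is worded as a requirement: "First start the infusion at one quarter the hourly rate x 15 minutes", then 50% for 15 minutes, and "then increase the rate to complete the remaining infusion within one hour of the start time".

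Neither schedule caps the rate of the last step. The full hourly rate from the outset is allowed only for later infusions, and only if there is no further reaction. The paragraph ends: "Consultation with study team is indicated to determine if steroids are indicated per Regimen 2". Further down, the text on recurrent reactions makes later dexamethasone discretionary "for recurrent (i.e. occurring despite slowing infusion as discussed above) grade 2 reactions but is not mandated", which treats the preceding steps as a slowing of the infusion.

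**The concern.** Two slow quarter-hours inside an unchanged one-hour limit do not slow the infusion as a whole. They move most of the dose into the second half. The mean rate over the hour is no lower than the standard one, and the last half hour is faster.

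The patients concerned are those who have just reacted, probably at the standard rate. Followed exactly, the rule gives them drug and Cremophor EL above that rate for half of the next infusion. If such a patient reacts again, the record will suggest a reaction despite slowing, when the second half had been sped up. What is at stake is the safety of a few patients and the clarity of a mandatory nursing instruction. No estimate or test in the trial depends on it.

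**Working it through.** **Inputs.** Standard infusion of one dose in 60 minutes (3.2.2). Steps of 25% for 15 minutes and 50% for 15 minutes, with completion within 60 minutes of the start (3.2.4). Doses of 6 and 4.5 mg/m² (3.3.1). Stability of 6 hours after final dilution (8.1.9). The protocol states no figure for the last step, so there is none to reproduce. I take the hourly rate to mean the standard one-dose-per-hour rate.

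**Next-day infusion (full dose).**

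- Given by 30 minutes: 0.25 × 15/60 + 0.50 × 15/60 = 0.0625 + 0.125 = 0.1875.
- Remaining: 1 − 0.1875 = 0.8125, in at most 0.5 h.
- Mean rate needed: 0.8125 / 0.5 = 1.625 times standard.
- At 6 mg/m²: 6 × 1.625 = 9.75 mg/m²/h. At 4.5 mg/m²: 4.5 × 1.625 = 7.31 mg/m²/h.
- Jump from the preceding step: 1.625 / 0.5 = 3.25-fold.
- Finishing earlier needs more: 0.8125 / (25/60) = 1.95 times standard over 25 minutes.

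**Same-day restart.** If the reaction occurs *t* minutes into a standard-rate infusion, the fraction left is *f* = 1 − *t*/60. The last half hour must average (*f* − 0.1875)/0.5. With the last step capped at the standard rate, the restart takes 30 + (*f* − 0.1875) × 60 minutes.

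| Reaction at (min) | Fraction left | Last half hour needed, as written | Restart if capped (min) |
|---|---|---|---|
| 5 | 0.9167 | 145.8% | 73.75 |
| 10 | 0.8333 | 129.2% | 68.75 |
| 15 | 0.75 | 112.5% | 63.75 |
| 18.75 | 0.6875 | 100% | 60.00 |
| 30 | 0.5 | 62.5% | 48.75 |

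The restart therefore exceeds the standard rate only when more than 68.75% of the dose is left, that is, after a reaction in about the first 19 minutes. After a later reaction it can be slower, as the text intends.

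**With a cap at the standard rate.** A full next-day dose takes 30 + 0.8125 × 60 = 78.75 minutes, which is 18.75 minutes more than now. For a same-day restart after a reaction in the first 48.75 minutes, the minutes before the reaction plus the capped restart also come to 78.75 (for example 5 + 73.75). That leaves 360 − 78.75 = 281.25 minutes of the 6-hour limit for the interruption and handling.

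**Absolute rates.** Section 1.2.4 reports ixabepilone at 50 mg/m² over 1 hour (50 / 9.75 = 5.1 times the rate derived here) and 40 mg/m² over 3 hours (40 / 3 = 13.3 mg/m²/h). The 9.75 mg/m²/h is high only relative to the rate at which this patient reacted.

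**The case against.** Nobody need dispute the arithmetic. The case against concerns intent, consequence and size.

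*The hour may run from the last step-up.* That would give 81.25% of standard and 90 minutes in total. The text counts from the start time, however, and the parallel sentence counts from the restart time. If the other meaning was intended, the wording still needs changing.

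*Only the same-day restart is expressly called slower.* This stands. The next-day paragraph speaks only of a rate schedule, and its link to slowing is the later back-reference, which could be read as covering the restart alone. A graded start within the usual hour is a possible intent. Even so, the next-day rule comes before any return to the full hourly rate, so a second half above that rate is hard to explain as deliberate.

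*Other provisions protect the patient.* They do so in part. Regimen 4 in section 3.2.3 starts at 25% of the previous rate for an hour and may extend to 6 hours from dilution, and it overlaps for some of these patients. It is only a suggestion, for Grade 2 or greater reactions despite premedication, and section 3.2.4 says that Regimens 1 to 4 come from the one-day schedule. Stepping up to Regimen 2 premedication and consulting the study team about steroids do not change the rate.

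*A reader might infer that the error triggers the stop and 24-hour delay.* The documents do not support this. Those measures apply to any recurrent Grade 2 reaction, whatever the rate. The remark about slowing sits only in the sentence on discretionary dexamethasone, so no steroid consequence follows either.

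*Harm is not shown.* This stands. The documents hold no data relating rate to reactions, the absolute rate is below others cited, and these patients have already completed a resumed infusion.

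**Conclusion.** The point holds as a minor safety correction. As written, the mandatory next-day schedule runs the last 30 minutes at 162.5% of the standard rate or more, at either dose level, and nothing else in the protocol caps it. This conflicts with the protocol's own remedy of slowing. The same-day restart shares the fault only after an early reaction.

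The arithmetic rests on the stated steps and on the reading of hourly rate given above. That the patient had reacted at the standard rate, and that a faster second half could provoke another reaction, are inferences; the second rests on the protocol's own use of slowing. Few patients would be affected, and the number cannot be derived from the documents. Section 1.2.4 describes reactions as very rare with daily dosing over five days, and the next-day rule covers only reactions on Days 1 to 4 that were resumed without recurrence.

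It would go too far to conclude that the rate is dangerous in itself, or that the response endpoint or the two-stage design is affected.

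**What to change.** In both sentences of section 3.2.4, replace the one-hour limit on the last step with: *at no more than the standard hourly rate until complete, within the 6-hour stability limit*. A full next-day dose then runs at 25% for 15 minutes, 50% for 15 minutes and 100% for 48.75 minutes. Leave Regimen 4 as the suggested slower option for Grade 2 or greater reactions despite premedication.

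The cost is the rewording of two sentences and of the matching nursing and pharmacy orders. An affected next-day infusion takes about 19 minutes longer. For a same-day restart after an early reaction, total infusing time also reaches about 79 minutes, but the restart itself overruns its present one-hour limit by less than 19 minutes. Sample size, endpoints and analysis do not change.

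### Sections 3.2.3 and 3.2.4 conflict on hypersensitivity: Grade 4 is carried into re-challenge wording, and a Grade 3 reaction on Regimen 1 falls under two different steroid instructions (minor)

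*Combined protocol and SAP*

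**What the plan says.** **Grade 4.** Section 3.2.4 has one paragraph for several severities. It opens "Recurrent CTCAE Grade 2 or CTCAE Grade 3 or 4 Allergic/Hypersensitivity Reactions: Stop the infusion", lists acute treatment, and then says "Further treatment should be delayed 24 hours". It goes on: "Prior to re-challenge and with all subsequent cycles, give both an H1 and H2 blocker intravenously plus dexamethasone 20 mg x 2 doses", timed "orally or intravenously) 12 and 6 hours pre ixabepilone". None of these sentences is limited by grade. The next line reads "Grade 4 (anaphylaxis): Discontinue therapy. Do not attempt re-challenge". Item 3 of Section 3.9 lists a Grade 4 hypersensitivity reaction as a reason to stop treatment.

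**Steroid premedication.** Section 3.2.3 sets out four regimens:
- Regimen 1 (oral H1 and H2 antagonists) is the routine one.
- A patient who reacts on Regimen 1 and is re-treated should receive Regimen 2, which includes dexamethasone 20 mg IV about 30 to 45 minutes before each infusion. No grade limit is given.
- A patient who reacts again on Regimen 2 moves to Regimen 3.
- Regimen 4 is a suggested way to re-treat after a reaction of Grade 2 or higher on any of the first three. It has no upper grade limit.

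**Notes in 3.2.4.** One says "The administration of dexamethasone immediately prior to ixabepilone is unlikely to be effective". Another says that Regimens 1 to 4 "are standard for ixabepilone that is given as a one day infusion every 3 weeks, not a daily x 5 schedule". A third leaves it to the Principal Investigator whether "a dose reduction to 5 mg dexamethasone administered intravenously prior to each dose of ixabepilone may be attempted".

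**The concern.** These rules are read at the bedside, during or just after a reaction, by staff who may rarely have seen one with this drug. Two instructions cannot both be followed as written.

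First, the paragraph that names Grade 4 proceeds to a delay and re-challenge, while the line below it forbids re-challenge.

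Second, after a Grade 3 reaction on Regimen 1, staff who work from 3.2.3 would give one dexamethasone dose shortly before the infusion. Staff who work from 3.2.4 would give two doses many hours before it. At stake is the protection of the next infusion in a patient who has just had a severe reaction. The response endpoint, the two-stage rule and the sample size are not involved.

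**Working it through.** The plan gives no figure to reproduce here. The check compares the texts and adds up doses.

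**1. Grade 4**

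| Place | Instruction that reaches Grade 4 |
|---|---|
| 3.2.4, paragraph on recurrent Grade 2, Grade 3 or Grade 4 | Stop, treat, wait 24 hours, premedicate before re-challenge and in later cycles |
| 3.2.3, Regimen 4 | Suggested method of re-treatment after Grade 2 or higher, no upper limit |
| 3.2.4, next line | End therapy, no re-challenge |
| 3.9, item 3 | Off treatment |

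The acute steps in the first row suit Grade 4. The delay and re-challenge sentences do not, and nothing in that paragraph removes Grade 4 from them. The two stop rules settle the intent.

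**2. Grade 3 reaction on Regimen 1, patient re-treated**

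| Source | Wording | Dexamethasone before one infusion | Timing |
|---|---|---|---|
| 3.2.3, Regimen 2 | directive | 1 × 20 = 20 mg, IV | 30 to 45 minutes before |
| 3.2.4 | directive | 2 × 20 = 40 mg, oral or IV | 12 and 6 hours before |
| 3.2.3, Regimen 4 | suggested only | 4 × 20 = 80 mg, oral or IV | every 6 hours, last dose 30 minutes before |

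The same patient meets the trigger for both directive rows, because the move to Regimen 2 applies to a reaction of any grade and the 3.2.4 rule names Grade 3. The directive texts differ by 40 / 20 = a factor of two in dose, and by hours in timing.

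**3. Does any sentence rank them?**
- Section 3.2.3 refers to 3.2.4 only for immediate management, and sets re-treatment premedication itself.
- The note on one-day dosing says where Regimens 1 to 4 come from. It neither withdraws them nor says that 3.2.4 overrides them, and 3.2.3 keeps Regimen 1 for routine use.
- The mention of Regimen 2 within 3.2.4 concerns patients who resumed the infusion without a further reaction. It is not part of this conflict.

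**4. Steroid load per cycle**

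Section 3.2.4 says that dexamethasone, if used, is at first given before all doses. There are five infusions per cycle:
- Regimen 2: 5 × 20 = 100 mg
- 3.2.4 schedule: 5 × 40 = 200 mg
- 5 mg option: 5 × 5 = 25 mg

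The note in 3.2.4 itself anticipates 100 mg or more every three weeks, so the higher total is within what the protocol already contemplates.

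**The case against.** **Grade 4 is handled on the page.** A general paragraph followed by a specific exception is ordinary drafting, and Section 3.9 repeats the exception. This stands as to intent, and makes the first part close to editorial. A reader might infer that the protocol permits re-challenge after Grade 4. It does not: two explicit rules forbid it, Regimen 4 describes how to re-treat rather than whether to, and Section 3.3.3 defaults to no restart after a Grade 4 non-hematologic toxicity. What remains is a paragraph whose literal wording disagrees with the line below it.

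**There are grounds to prefer 3.2.4.** It is grade-specific, it speaks to later cycles, and the note says that the regimens were written for another schedule. This narrows the ambiguity but does not remove it, because no sentence gives precedence.

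**The spread of schedules can be overstated.** A reader might count three competing instructions and a fourfold dose range (20 to 80 mg). Regimen 4 is only suggested, so the conflict between directive texts is twofold. A reader might also treat recurrent Grade 2 exactly like Grade 3. The same paragraph leaves dexamethasone in later cycles for recurrent Grade 2 to the investigator, so for that grade the requirement holds at most for the first re-challenge.

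**Reactions are rare on this schedule.** Section 1.2.4 reports none in the 27-patient phase I study of daily × 5 dosing and calls them very rare in the institution's experience. That supports a minor rating. A reader might try to bound the risk from the rates quoted there for paclitaxel and cyclosporine. Those are other products with different outcome definitions, and they give no bound for this drug or for the chance of a wrong instruction being followed.

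**Conclusion.** The point holds as a minor safety inconsistency that is wrong as written. The Grade 4 part is a contradiction in wording whose intended answer is clear. The Grade 3 part is less well resolved: two directive texts differ twofold in dexamethasone dose before an infusion (20 mg against 40 mg) and in timing (under an hour against 12 and 6 hours), with no stated precedence.

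This rests on reading both texts as applying to a re-treated patient with a Grade 3 reaction on Regimen 1, which their triggers allow. It does not rest on the note about dexamethasone given immediately beforehand. That term is undefined. Taking it to cover 30 to 45 minutes is reasonable but is an assumption, and the schedules differ without it. The documents do not allow an estimate of how often the conflict would matter. There is no effect on the two-stage design, sample size or error rates.

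**What to change.** 1. In 3.2.4, keep the acute steps for Grade 4, but limit the delay and re-challenge sentences to recurrent Grade 2 and Grade 3.
2. In 3.2.3, add an exception for Grade 4 to Regimen 4, and otherwise leave its scope as it is.
3. In 3.2.3, state that after a Grade 3 reaction the 3.2.4 schedule (20 mg twice, oral or IV, at 12 and 6 hours before) replaces Regimen 2. Describe the schedule in full rather than by pointing to Regimen 3, whose dexamethasone is oral only. Such a pointer would drop the IV route.
4. Keep the investigator's discretion over later-cycle dexamethasone for recurrent Grade 2, and the Principal Investigator's 5 mg option.

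The choice of schedule is the sponsor's clinical decision. The proposal follows the protocol's own grade-specific text. The cost is a wording amendment, with no new procedure and no change to the sample size. The downside is a steroid load of up to 200 mg rather than 100 mg per cycle if given before all five doses, which 3.2.4 already implies. The 5 mg option allows a reduction to 25 mg.
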